2.2 Secondary Objectives

Analytical sub-aims of the protocol are to: 1) Describe characteristics of women who under-attend for cervical cancer screening in a safety net health system; 2) Explore patterns of detection and treatment of cervical pre-cancers across study arms; 3) Compare characteristics of screening participants across study arms.

We will also conduct a nested study within the randomized controlled trial to assess acceptability of and experiences with self-sample HPV testing among underscreened women in our safety net health system. The nested study has two components: a telephone survey and in-depth

qualitative interviews. In the remainder of the protocol these will be referred to as "Telephone Survey" and "Qualitative Interviews."

Because of the COVID-19 pandemic, we have revised some elements of the trial, as reflected throughout the protocol. One of these revisions includes expansion of analytic sub-aim 1 (above) to include monitoring of ambulatory, and more specifically, primary care utilization in addition to cervical cancer screening. The COVID-19 era sub-aims are: 1) To compare changes in cervical cancer screening and primary care utilization (overall and by face-to-face vs. telehealth modalities) among socioeconomic, racial/ethnic, and nativity subgroups in the 12-months following the COVID-19 emergency declaration; and 2) To compare the role of individual and neighborhood-level factors on cervical cancer screening and primary care utilization (overall and modality-specific) before and after the COVID-19 emergency declaration. In the remainder to the protocol, we will refer to COVID-19 era analytic sub-aims.

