COVID-19 era analytic sub-aim: 1) We will use descriptive statistics (bivariable tables and chi-square/Fisher's exact tests) to compare characteristics of women who do/do not attend for cervical cancer screening, primary care (all types), and telehealth-specific primary care. We will compare proportions at baseline (February 2020, pre-pandemic), and at 6- and 12-months post COVID-19 emergency declaration (July 2020 and February 2021). Independent multivariable Poisson regression models will be used to assess the independent association between cervical cancer screening and primary care utilization and participant characteristics.

Additional variables will be collected to meet the aims of the NIH-funded supplement (3R01MD013715-04S1) to the parent self-sampling trial: HIV status, Preventive Care Gap Score, Enrollment in MyHealth portal, History of COVID-19 diagnosis, HPV vaccination status and Risk of Admission or ED visit.

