4.1 Eligibility Criteria

Randomized Controlled Trial. To be eligible for randomization, women must 1) be age 30-65 years; 2) have no history of hysterectomy or cervical cancer; 3) have at least 2 visits to ambulatory care within Harris Health System in the past 5 years; 4) be enrolled in a healthcare coverage or financial assistance plan accepted by Harris Health or have been enrolled in a Harris Health coverage plan in the past 12 months; 5) not have a history of cervical dysplasia in the past 3.5 years; and 6) have not had a Pap test in the past 3.5 years or Pap/HPV co-test in the past 5.5 years. A 6-month grace period is added to allow time for women to respond to opportunistic usual care strategies (i.e., in-clinic EMR-flagging and video-based patient education).

For analytical sub-aim 1 (Describe characteristics of women who under-attend for cervical cancer screening in a safety net health system), inclusion criteria are broadened to include all women who meet inclusion criteria 1-4, but not criteria 5 (i.e., women of all screening status will be included in the analysis).

Telephone Survey. To be eligible for the telephone survey, women must 1) have participated in RCT (and thus have met RCT inclusion criteria above) and 2) have been randomized to Arm 2 or 3.

Qualitative Interviews To be eligible for the qualitative interviews, women must 1) have participated in RCT (and thus have met RCT inclusion criteria above); 2) have been randomized to Arm 2 or 3; and 3) had an HR-HPV positive test result.

For COVID-19 era analytics sub-aims, inclusion criteria are broadened to include women ages 18-65 years who meet inclusion criteria 3 and 4 (i.e., we will include all women 18-65 years who have used Harris Health ambulatory care services at least twice in the past 5 years and who have a healthcare coverage plan accepted by Harris Health).

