The risks to privacy are small and this waiver will not adversely affect the patients' privacy rights or welfare. PHI will be collected to assess eligibility for participation and to determine screening outcomes among control group participants and intervention group participants who decline to use the self-sampling kit. Once these chart reviews are complete, the dataset will be stripped of PHI. Data will be securely stored on password-protected database servers.

Waiver to determine subject eligibility: There are over 100,000 women who are age-eligible for cervical cancer screening within Harris Health System. Individually contacted them and seeking

consent to determine their eligibility for the study (based on their cervical cancer screening status) would be practically impossible.

Waiver for subjects enrolled in Arm 1: Requiring informed consent for a standard-of-care intervention, such as patient recall, would introduce substantial bias in terms of participation in the intervention. Ascertaining screening outcomes related to this standard-of-care intervention cannot be done without accessing and using PHI.

Waiver for subjects enrolled in Arms 2 and 3: Ascertaining screening outcomes cannot be done with accessing and using PHI. Individually contacting each participant to obtain consent for this review is not feasible.

Access to data will be limited and based on the role of personnel. Study personnel will only use necessary data, and will make every effort to minimize risk and protect confidentiality.

Sample receipt and subsequent test results will be recorded per standard of care in the patient's protected Harris Health electronic medical record. The study coordinator will securely access the Electronic Medical Record to extract relevant research data (sample receipt and outcome).

The extracted research information will be stored on secure, password-protected database on MDA servers. These servers are physically located in the MD Anderson data center and inside the MD Anderson firewall. Servers are managed by MDA informatics professionals in accordance with MDA guidelines.

Waiver of HIPAA Authorization

N/A

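### COVID-19 era sub-aim 1 sets July 2020 against a February baseline with no earlier-July comparator and no stated measurement window, so that contrast can mix season and calendar with the pandemic effect

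*Combined protocol and SAP*

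**What the plan says.** Section 2.2 Secondary Objectives gives COVID-19 era sub-aim 1 as "To compare changes in cervical cancer screening and primary care utilization (overall and by face-to-face vs. telehealth modalities) among socioeconomic, racial/ethnic, and nativity subgroups", the period being "in the 12-months following the COVID-19 emergency declaration". Sub-aim 2 looks at individual and neighbourhood factors "before and after the COVID-19 emergency declaration".

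Section 3.4 Data Analysis names three time points: "We will compare proportions at baseline (February 2020, pre-pandemic), and at 6- and 12-months post COVID-19 emergency declaration (July 2020 and February 2021". February 2020 is the only pre-pandemic value. The groups compared are women who do and do not attend for screening, for primary care of any type, and for telehealth primary care, using chi-square or Fisher's exact tests. The regression step reads: "Independent multivariable Poisson regression models will be used to assess the independent association between cervical cancer screening and primary care utilization and participant characteristics". It mentions no term for month or season and no offset for days open.

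The population is wider than the trial's. Under section 4.1, "inclusion criteria are broadened to include women ages 18-65 years who meet inclusion criteria 3 and 4". Its size is not given. Section 8 Potential Benefits says this work will show what the pandemic did to the use of screening and primary care.

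The plan does not say whether a proportion means attendance within the named month, attendance over a look-back period, or screening status on a date.

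**The concern.** A before/after contrast isolates the pandemic only if the two periods would otherwise have looked alike. July and February differ in length, in working days and possibly in seasonal demand. With no earlier July and no adjustment, whatever normally separates July from February is counted as pandemic effect at the six-month point.

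What is at stake is the July 2020 estimate of how far utilisation fell or recovered, overall and as an absolute change within subgroups. It bears directly on the purpose stated in section 8. It has no bearing on the randomised comparison of the three outreach arms.

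**Working it through.** The plan gives no rate, sample size or power for the COVID-19 sub-aims, so there is no design figure to reproduce. The check sizes the calendar component only.

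**Inputs.** The months come from section 3.4. Weekday and day counts come from the calendar.

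| Month | Calendar days | Weekdays | Weekdays less federal holidays |
|---|---|---|---|
| July 2019 | 31 | 23 | 22 |
| February 2020 | 29 | 20 | 19 |
| July 2020 | 31 | 23 | 22 |
| August 2020 | 31 | 21 | 21 |
| February 2021 | 28 | 20 | 19 |

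**Assumptions, none stated in the plan.** Clinics open Monday to Friday; a one-month window; a constant chance of attending per clinic day.

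**Step 1: ratio of clinic days.**
- July 2020 to February 2020: 23/20 = 1.15. Without federal holidays, 22/19 = 1.158. On calendar days, 31/29 = 1.069.
- February 2021 to February 2020: 20/20 = 1.00.
- July 2020 to July 2019: 23/23 = 1.00.

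**Step 2: effect on a proportion of women.** If a proportion p attends in a 20-day month, the proportion in a 23-day month with unchanged daily behaviour is q = 1 - (1 - p)^(23/20).

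| p (February) | q (July, no real change) | q/p | q - p |
|---|---|---|---|
| 1% | 1.15% | 1.149 | 0.15 points |
| 5% | 5.73% | 1.146 | 0.73 points |
| 10% | 11.41% | 1.141 | 1.41 points |
| 20% | 22.63% | 1.132 | 2.63 points |
| 30% | 33.65% | 1.122 | 3.65 points |

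The relative inflation is therefore about 12-15%, depending on the base rate.

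**Step 3: what it could hide.** On the scale of visit volume, a true fall d per clinic day appears as a monthly ratio of (1 - d) x 1.15. A 13% fall gives 0.87 x 1.15 = 1.00, which looks like no change. A 30% fall gives 0.70 x 1.15 = 0.805, which looks like 19.5%.

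**Step 4: subgroups.** Take one subgroup at 10% and another at 20%, neither truly changing. Their absolute changes differ by 2.63 - 1.41 = 1.22 points. Their relative changes barely differ: 1.132/1.141 = 0.992.

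**Step 5: would a test notice?** As an illustration only, take 100,000 women per time point as independent samples. Section 6.2.2 says "There are over 100,000 women who are age-eligible for cervical cancer screening within Harris Health System", which is not the same population. At p = 1%, a two-sided 0.05 test would flag the calendar artefact alone with probability 0.90. With 15,000 women the probability is 0.24 at p = 1% and 0.80 at p = 5%.

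**Step 6: the month labels.** February to July 2020 is 5 months and July 2020 to February 2021 is 7. The last two cannot be 6 and 12 months from one date at month resolution. The documents do not give the declaration date. If February 2021 is the twelve-month point, the six-month point is August 2020, and the weekday ratio to February 2020 drops to 21/20 = 1.05.

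**The case against.** The strongest objection is that the one-month window is an inference. Section 3.1 records primary care appointments at six months, which suggests a period running up to a time point. Section 2.2 presents the COVID-19 work as an expansion of analytic sub-aim 1, which section 3.4 analyses as screening status. A 12-month look-back, or a status measure, would largely remove the clinic-day and seasonal argument.

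That stands, and it is why the conclusion is conditional. It does not settle the matter, for three reasons:
- The sub-aim is worded in terms of attending and of utilisation, and an up-to-date status does not fit primary-care or telehealth visits.
- A six-month look-back would set February-July 2020 against September 2019-February 2020, so season would still be mixed in.
- A 12-month look-back for July 2020 would run from August 2019. Seven of its 12 months, through February 2020, would be pre-pandemic by the plan's own label, so the contrast would be diluted.

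The window has to be stated on any reading.

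A second objection is that sub-aim 1 compares changes between subgroups, and a factor common to all of them cancels in relative comparisons. This also stands, nearly exactly (step 4). But the plan does not commit to a relative comparison, and absolute changes and overall before/after statements remain exposed.

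A reader might go further and infer that the whole three-point comparison lacks a same-month baseline. It does not: February 2021 is set against February 2020, with 20 weekdays in each. A reader might also infer that any real fall in July is understated. Only the clinic-day part points that way; a seasonal dip in July would overstate the fall, and the documents hold no seasonal data. Nor do they show that season affects subgroups differently.

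**Conclusion.** The point holds for the July 2020 contrast only. As written, July 2020 is compared with February 2020, with no earlier July and no adjustment for month or clinic days. If the proportions describe attendance in or around the named month, the contrast cannot separate season and calendar from the pandemic.

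Under the assumptions listed in the working, the calendar part alone is a relative rise of about 12-15%. That figure should not be read as an established bias. It depends on the undefined window, on a clinic calendar the documents do not give, and on a July label that does not fit beside February 2021; at August 2020 the clinic-day excess would be 5%. The seasonal part has unknown size and direction.

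The matter is modest in weight, confined to a secondary observational analysis, and cheap to correct.

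**What to change.** Revise the COVID-19 paragraph of section 3.4 to:

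1. State the measurement window for each outcome (screening, all primary care, telehealth): the dates covered, and whether it is attendance or status.
2. Extract the same month of 2019 as comparator for the six-month point (July 2019 if July 2020 is kept), so that each post-declaration point is compared with the same calendar month before the pandemic. July 2019 and July 2020 have 23 weekdays each; if another month is chosen, check the clinic days.
3. Reconcile the six- and twelve-month labels with the named months, and give the declaration date they are counted from. If the twelve-month point moves from February, it needs its own same-month comparator.
4. Say whether subgroup differences in change will be judged on the relative or the absolute scale.

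The cost is a slightly longer date range in the record extraction, a revised paragraph, and a rule for applying the visit and coverage criteria of section 4.1 (two visits in five years, plan enrolment) at the 2019 date. The setting description in section 3.1 says monthly record reports can already be produced. A monthly series with a segmented model, month terms and a clinic-day offset would be informative but is optional; the same-month comparator meets the point.

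### The COVID-19 sub-aims ask whether change differs by subgroup and whether factor effects differ before and after the declaration, but the planned Poisson models contain no contrast that tests either, and their variance method is unstated

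*Combined protocol and SAP*

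**What the plan says.** Section 2.2 (Secondary Objectives) sets two COVID-19 era sub-aims. The first is "To compare changes in cervical cancer screening and primary care utilization (overall and by face-to-face vs. telehealth modalities) among socioeconomic, racial/ethnic, and nativity subgroups" over the year after the declaration. The second is "To compare the role of individual and neighborhood-level factors on cervical cancer screening and primary care utilization", with the periods before and after the declaration set against each other.

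Section 3.4 (Data Analysis), in its COVID-19 paragraph, gives three pieces of analysis:

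- Tables with chi-square or Fisher's exact tests to "compare characteristics of women who do/do not attend for cervical cancer screening, primary care (all types), and telehealth-specific primary care".
- A comparison over time: "We will compare proportions at baseline (February 2020, pre-pandemic), and at 6- and 12-months post COVID-19 emergency declaration (July 2020 and February 2021").
- The regression, relating these to participant characteristics: "Independent multivariable Poisson regression models will be used to assess the independent association between cervical cancer screening and primary care utilization".

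The paragraph numbers only an item 1. It describes no separate analysis for the second sub-aim and does not mention neighborhood-level factors. It names no time variable, interaction term, robust variance or method for repeated observations. Section 4.1 defines the COVID-19 population by age, past ambulatory use and coverage. It does not say whether this is one fixed cohort or a new cross-section at each date.

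**The concern.** Both sub-aims are questions about differences of differences. The first asks whether one subgroup's change differs from another's. The second asks whether a factor's effect differs between two periods. A model relating an outcome to participant characteristics estimates who attends more or less. It does not estimate whether that gap widened or narrowed. Without a stated contrast, the conclusion would rest on inspecting proportions or on comparing p-values from separate fits, and neither is a test of differential change.

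Precision raises a further question. Attendance is described as a yes/no outcome, and the ordinary Poisson variance is larger than the true variance of such an outcome. An analysis looking for disparities would then tend to overlook them. If utilization is instead a visit count, overdispersion would push the error the other way.

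**Working it through.** The plan gives no sample size, prevalence, correlation or power for these sub-aims, so there is no figure to reproduce. The first two steps rest on the text alone. The later steps use assumed inputs.

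**1. Question against model.** Write the outcome model on the log scale, with S for a subgroup or factor and T for date or period:

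log E(Y) = a + b·S + c·T + d·S·T

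Sub-aim 1 asks about d with S a subgroup and T the date. exp(d) is the ratio of the two subgroups' relative changes. Sub-aim 2 asks about d with S an individual or neighborhood factor and T before or after. The regression in Section 3.4 describes only b. The comparison of proportions across dates describes only c, and the tables of attenders against non-attenders do not supply d.

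**2. Would separate models per date supply it?** They give b at each date, so d can be estimated as b(later) − b(baseline). Its variance is Var(b later) + Var(b baseline) − 2·Cov. The plan states no such comparison. If women recur across dates, separate fits do not give the covariance.

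**3. Yes/no outcome, one date, two equal groups of size n.** For the log risk ratio:

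- Model-based Poisson variance: 1/(n·p1) + 1/(n·p2)
- True variance: (1−p1)/(n·p1) + (1−p2)/(n·p2)

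With p1 = p2 = p, the ratio of standard errors is 1/√(1−p). The actual size of a nominal two-sided 5% test is 2·[1 − Φ(1.96/√(1−p))].

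| Assumed p | SE ratio | Actual test size |
|---|---|---|
| 0.10 | 1.054 | 3.9% |
| 0.20 | 1.118 | 2.8% |
| 0.30 | 1.195 | 1.9% |
| 0.50 | 1.414 | 0.6% |

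As an illustration, take the national screening proportions in Section 1.2 (63.7% and 79.5%). The ratio is √[(1/0.637 + 1/0.795)/(0.363/0.637 + 0.205/0.795)] = √(2.828/0.828) = 1.85. The error at a single date is always conservative. It is small for rare outcomes and large for common ones.

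**4. If utilization is a visit count.** With variance φ times the mean and φ > 1, the model-based standard error is too small, by the factor 1/√φ. The plan gives no basis for a value of φ.

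**5. Recurring women.** If eligibility were reassessed at each date, five-year look-back windows ending in February 2020 and February 2021 would share four of five years. Substantial overlap is therefore likely, though not stated. Correlation matters wherever dates are compared or pooled. It does not enter a model fitted to one date with one row per woman.

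**6. Does the remedy work?** Three dates with 1,000 women and no true effects were simulated 400 times per setting, at prevalences 0.1, 0.3 and 0.6 with correlated outcomes. Poisson regression with variance clustered on woman rejected in 3.5% to 6.0% of runs for a between-women effect and in 3.0% to 6.25% for subgroup-by-time. The nominal level is 5% and simulation error is about 1.1 points. Model-based variance on the same stacked data gave 1.25% to 13.0% and 0% to 2.0%.

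**The case against.** The strongest reply is that most of the precision argument is read from silence. Section 3.4 names a model family and does not rule out robust variance; the remedy is itself a Poisson model. *Independent* may mean one model per outcome or one per date, and in the second case no within-woman correlation enters any single fit. *Utilization* may be a count, for which Poisson is a natural choice. The sub-aims are observational, carry no power claim, and lie outside the randomized comparison. Much of this stands, and it limits the precision point to a conditional one.

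A reader might go further and infer that the same women are followed at all three dates, that ordinary Poisson variance will be used, and that the reported intervals will therefore be wrong. The documents support none of these as fact. A reader might also compute 1/√((1−p)(1−ρ)) and conclude that standard errors for change are 25% to 54% too large (p = 0.2 to 0.3, within-woman correlation ρ = 0.2 to 0.4). That presumes the dates stacked in one model with a time term, which Section 3.4 does not describe. Even when stacked, the direction depends on the contrast. For a between-women factor, 1/√((1−p)(1+2ρ)) runs from 0.71 (p = 0.1, ρ = 0.6) to 1.54 (p = 0.7, ρ = 0.2), and is 1.01 at p = 0.3, ρ = 0.2.

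The reply does not reach the main point. On any reading of *Independent*, and for yes/no or count outcomes alike, no subgroup-by-time or factor-by-period contrast is stated.

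**Conclusion.** The point holds in two parts of unequal strength. First, and without any assumption, the COVID-19 analysis in Section 3.4 does not test what Section 2.2 asks. Differential change by subgroup has no contrast, and the before-and-after comparison of factors has no described analysis.

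Second, and conditionally, if attendance is analysed as yes/no with model-based Poisson variance, single-date standard errors are 5% to 41% too large for prevalences of 10% to 50%, and a nominal 5% test runs at 3.9% down to 0.6%. The prevalences are assumptions. The claim supported is that the plan leaves the variance method and the handling of recurring women unstated, not that its intervals are wrong. The matter is worth settling before these sub-aims are analysed. It does not bear on the trial's primary result.

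**What to change.** Revise the COVID-19 paragraph of Section 3.4 as follows:

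- Say for each outcome whether it is yes/no attendance or a visit count, and whether the dates draw on a fixed cohort or repeated cross-sections.
- For each yes/no outcome, fit one modified Poisson (log-link) GEE over the three dates, clustered on woman with robust standard errors. Clustering on woman serves either sampling design.
- For sub-aim 1, include time-by-subgroup terms and report the ratio of change between subgroups with its interval.
- For sub-aim 2, add its own numbered item with factor-by-period terms, and say how correlation among women in the same neighborhood is handled.
- If utilization is analysed as visit counts, use the same model; the robust variance then allows for overdispersion.

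The cost is plan wording and a little more analysis work in standard software. No new data are needed.
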